7.4.5.2. Exposure during Breastfeeding

An exposure during breastfeeding occurs if:

- A female patient is found to be breastfeeding while receiving or after discontinuing study treatment.
- A female is found to be breastfeeding while being exposed or having been exposed to study treatment (ie, environmental exposure). An example of environmental exposure during breastfeeding is a female family member or healthcare provider who reports that she is breastfeeding after having been exposed to the study treatment by inhalation or skin contact.

The investigator must report exposure during breastfeeding to Pfizer Safety within 24 hours of the investigator's awareness, irrespective of whether an SAE has occurred. The information must be reported using the CT SAE Report Form. When exposure during breastfeeding occurs in the setting of environmental exposure, the exposure information does not pertain to the patient enrolled in the study, so the information is not recorded on a CRF. However, a copy of the completed CT SAE Report Form is maintained in the investigator site file.

An exposure during breastfeeding report is not created when a Pfizer drug specifically approved for use in breastfeeding women (e.g., vitamins) is administered in accord with authorized use. However, if the infant experiences an SAE associated with such a drug, the SAE is reported together with the exposure during breastfeeding.

7.4.5.3. Occupational Exposure

An occupational exposure occurs when a person receives unplanned direct contact with the study treatment, which may or may not lead to the occurrence of an AE. Such persons may include healthcare providers, family members, and other roles that are involved in the trial patient's care.

The investigator must report occupational exposure to Pfizer Safety within 24 hours of the investigator's awareness, regardless of whether there is an associated SAE. The information must be reported using the CT SAE Report Form. Since the information does not pertain to a patient enrolled in the study, the information is not recorded on a CRF; however, a copy of the completed CT SAE Report Form is maintained in the investigator site file.

7.4.6. Cardiovascular and Death Events

All cardiovascular events will be managed per the dose modification guidelines in [Appendix 2](#) and [Appendix 3](#). Additionally, cardiovascular events will be reported per AE and SAE reporting guidelines and ECG criteria, as detailed in [Section 7.4](#) and [Section 7.3.6](#), respectively. AEs and SAEs that result in death will be reported per the reporting guidelines as outlined in [Section 7.4](#).

7.4.7. Disease-Related event and/or Disease-Related Outcomes Not Qualifying as AEs or SAEs

Not applicable

7.4.8. Adverse Events of Special Interest

See [Section 2.2.3](#) Clinical Safety of Combination Encorafenib and Binimetinib for descriptions of AESIs.

7.4.8.1. Lack of Efficacy

Lack of efficacy is reportable to Pfizer Safety only if associated with an SAE.

7.4.9. Medical Device Deficiencies

Not applicable

7.4.10. Medication Errors

Medication errors may result from the administration or consumption of the study treatment by the wrong patient, or at the wrong time, or at the wrong dosage strength.

Exposures to the study treatment under study may occur in clinical trial settings, such as medication errors.

Safety Event	Recorded on the AE CRF	Reported on the CT SAE Report Form to Pfizer Safety Within 24 Hours of Awareness
Medication errors	Only if associated with an AE or SAE	Only if associated with an SAE

Medication errors include:

- Medication errors involving patient exposure to the study treatment;
- Potential medication errors or uses outside of what is foreseen in the protocol that do or do not involve the study patient.

In the event of a medication dosing error, the sponsor should be notified within 24 hours.

If applicable, any associated AE(s), serious and nonserious, are recorded on the AE page of the CRF.

Medication errors should be reported to Pfizer Safety within 24 hours on a CT SAE Report Form **only when associated with an SAE**.

7.5. Product Complaints

The Sponsor collects product complaints on study drugs/treatments used in clinical studies to ensure the safety of study patients, monitor quality and facilitate process and product improvements.

All product complaints associated with material packaged, labeled and released by the Sponsor (or designee) will be reported to the Sponsor. All product complaints associated with other study material will be reported directly to the respective manufacturer.

The Investigator or his/her designee is responsible for reporting a complete description of the product complaint via email or other written communication to the Sponsor contact or respective manufacturer within 1 business day of discovery. Any AE associated with a product complaint should be recorded as described in Section 7.4.4 and Section 7.4.5.

If the Investigator is asked to return the product for investigation, he/she will return a copy of the product complaint communication with the product.

7.6. Treatment of Overdose

There is no antidote known to over dosage either encorafenib or binimetinib. Supportive measures should be instituted.

In the event of an overdose, the investigator/treating physician should:

1. Contact the medical monitor within 24 hours.

2. Closely monitor the patient for any AEs/SAEs and laboratory abnormalities for at least 5 half-lives or 28 calendar days after the overdose of study treatment (whichever is longer). Closely monitor the patient for any AEs/SAEs.
3. Document the quantity of the excess dose as well as the duration of the overdose in the CRF.
4. Overdose is reportable to Safety **only when associated with an SAE**.

Decisions regarding dose interruptions or modifications will be made by the Investigator in consultation with the Sponsor Medical Monitor based on the clinical evaluation of the patient.

7.7. Pharmacokinetic Assessments

7.7.1. Blood Sample Collection

Blood samples (~4 mL each) for plasma PK analysis of encorafenib, its metabolite (LHY746), binimetinib and the active metabolite of binimetinib (AR00426032) will be collected from all patients enrolled in the Safety Lead-in portion of the study as shown in [Table 12](#). If the high-dose regimen is determined to be safe and patients are randomized to the high-dose and standard-dose treatments in the Phase 2 portion of the study, PK samples will also be collected from all Phase 2 patients as shown in [Table 12](#). However, if the high-dose regimen is determined not to be safe in the Safety Lead-in, PK samples will be collected from all Phase 2 patients as shown in [Table 13](#) using a reduced sampling schedule.

In addition to PK samples stated above, blood samples for PK may be requested for patients experiencing unexpected or serious adverse events; with evidence of disease progression; or with other events where PK sampling is considered useful (upon agreement between investigator and Sponsor). More than 1 PK sample per patient may be collected throughout the study; however, the total blood volume of additional PK samples collected per patient should not exceed 20 mL (ie, no more than 5, 4 mL samples).

Study visits for PK sampling should be scheduled in the morning so that proper predose and postdose PK blood samples can be collected. On the PK visit days, the morning doses of encorafenib and binimetinib will be taken at the study site at approximately the same time, only after collecting the predose PK sample. Predose sampling information will include the date and exact time of the most recent previous dose of encorafenib and binimetinib (except Cycle 1 Day 1), including the dose amount taken. Postdose sampling information, only needed for days with postdose PK sampling (i.e., Cycle 1 Day 1 and Cycle 1 Day 15), will include the date and exact time of the morning dose, including the dose amount taken. Except for the Cycle 1 Day 1 PK samples, which have to be obtained on the scheduled day, other PK samples may be obtained \pm 1 day from the scheduled date.

If vomiting occurs within 4 hours following study drug administration on the day of PK sampling, no additional study treatment will be taken to replace the material that has been vomited and it is recommended that no more PK samples be taken after the emesis occurs. Vomiting that occurs on Cycle 1 Day 1 and Day 15 will be noted in the PK eCRF. Further

doses should be administered with premedication with antiemetic medications. Cycle 1 Day 15 PK sampling that was compromised due to emesis will be repeated on Cycle 2 Day 1 after premedication with antiemetics.

Blood will be collected in accordance with institutional guidelines. Any sampling problems will be noted in the eCRF and on appropriate source documentation. Complete instructions for sample processing, handling and shipment will be provided in the Laboratory Manual.

CCI [REDACTED]

Table 12. Pharmacokinetic Blood Sample Timing in the Safety Lead-in Portion and in the Phase 2 Portion When the High Dose Regimen is Tested

Study Visit	Timing of Sample
Cycle 1 Day 1	
• 0.5 hours (\pm 5 min) postdose• 1.5 hours (\pm 5 min) postdose• 3 hours (\pm 10 min) postdose• 6 hours (\pm 20 min) postdose
Cycle 1 Day 15	
• Predose (within 30 minutes of dose)• 0.5 hours (\pm 5 min) postdose• 1.5 hours (\pm 5 min) postdose• 3 hours (\pm 10 min) postdose• 6 hours (\pm 20 min) postdose
Cycle 2 Day 1	
• Predose (within 30 minutes of dose)
Cycle 3 Day 1	
• Predose (within 30 minutes of dose)

Table 13. Pharmacokinetic Blood Sample Timing in the Phase 2 Portion When Only the Standard Dose Regimen is Tested

Study Visit	Timing of Sample
Cycle 1 Day 1	
• 1.5 hours (\pm 15 min) postdose
Cycle 2 Day 1 ¹	
• Predose (within 30 minutes of dose)• 1.5 hours (\pm 15 min) postdose
Cycle 3 Day 1	
• Predose (within 30 minutes of dose)• 1.5 hours (\pm 15 min) postdose

¹ Seven days of consecutive dosing at the starting doses (450 mg QD encorafenib + 45 mg BID binimetinib) are required prior to the intra-patient escalation (600 mg QD encorafenib + 45 mg BID binimetinib) and the escalation must start within 7 days of Cycle 2 Day 1 (see [Section 6.7.2.](#)). If the escalation occurs after Cycle 2 Day 1 the Cycle 2 Day 1 PK samples must be taken on the same day as the patient dose escalates.

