6.3.1.1. Plasma Concentrations of Encorafenib, LHY746, Binimetinib and AR00426032

Plasma concentrations of encorafenib, LHY746, binimetinib and AR00426032 will be quantitated at the time points indicated in Table 5:

Table 5: Pharmacokinetic Blood Sampling Times

Study Visit	Timing of Sample	Allowed Window ^a
C1D1	0.5 hours postdose	±5 min
	1.5 hours postdose	±5 min
	3 hours postdose	±10 min
	6 hours postdose	±20 min
C1D15	Predose	-30 min
	0.5 hours postdose	±5 min
	1.5 hours postdose	±5 min
	3 hours postdose	±10 min
	6 hours postdose	±20 min
C2D1 ^b	Predose	-30 min
C3D1	Predose	-30 min

^a Predose samples must be within 30 minutes of, but before, the following dose.

^b When more sampling is performed on C2D1 due to emesis on C1D15, the sample times and windows will be the same as for C1D15.

All plasma concentration values of each analyte for each patient in the PK set will be included in the bioanalytical plasma concentration listings. Individual concentration records will be flagged for the affected visit if any of the following occur on the day of PK sampling:

- a. Patient had vomiting:
 - within 4 hours following study drug administration on the day of PK sampling for post-dose samples (C1D1, C1D15 and C2D1 when more sampling is performed on that day due to emesis on C1D15); or
 - at any time over the preceding 24 hours for pre-dose samples (C1D15, C2D1 and C3D1).
- b. Prescription dosing was not performed for at least 4 consecutive days prior to C1D15, C2D1 or C3D1).
- c. Patient received a higher or lower dose compared to planned treatment
- d. PK sampling time was outside the allowed window (as shown in [Table 5](#)) or the elapsed time was not calculable.

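### Protocol 7.7.1 lists the days for recording the morning-dose time to fit Table 12, not Table 13, so that time may go unrecorded for two of three scheduled Phase 2 postdose PK samples, including all those at 600 mg

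*Protocol*

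**What the plan says.** Protocol Section 7.7.1 has two schedules. Table 12 serves the Safety Lead-in, and Phase 2 if the high dose is carried forward. Otherwise, "PK samples will be collected from all Phase 2 patients as shown in [Table 13](#) using a reduced sampling schedule". Table 13 is titled "Pharmacokinetic Blood Sample Timing in the Phase 2 Portion When Only the Standard Dose Regimen is Tested".

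The same section sets out the dosing information that goes with each sample:

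- **Predose:** "Predose sampling information will include the date and exact time of the most recent previous dose of encorafenib and binimetinib (except Cycle 1 Day 1", together with the amount of that earlier dose.
- **Postdose:** "Postdose sampling information, only needed for days with postdose PK sampling (i.e., Cycle 1 Day 1 and Cycle 1 Day 15", and this information "will include the date and exact time of the morning dose, including the dose amount taken".
- **Vomiting:** "Vomiting that occurs on Cycle 1 Day 1 and Day 15 will be noted in the PK eCRF".

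SAP Section 6.3.1.1 flags a concentration if the sampling time was outside its window "or the elapsed time was not calculable", and allows flagged points to be left out of summary statistics. It also flags vomiting "at any time over the preceding 24 hours for pre-dose samples (C1D15, C2D1 and C3D1".

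SAP Section 2 reports 3 DLTs in 9 evaluable Safety Lead-in patients and says that Phase 2 goes ahead without the high dose. Table 13 is therefore the schedule in use.

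**The concern.** The list of days in 7.7.1 was not brought into line with Table 13. It names a day on which Table 13 takes no sample (Cycle 1 Day 15) and leaves out two days on which it takes a postdose sample (Cycle 2 Day 1 and Cycle 3 Day 1).

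Those two days matter most for the escalated dose. Under Section 6.7.2, encorafenib goes to 600 mg QD at Cycle 2 Day 1 (+7 days), and the Table 13 footnote moves the Cycle 2 Day 1 samples to the escalation day if that is later. The Amendment 3 entry in Protocol Appendix 11 gives exposure changes from this escalation as the reason for the current Table 13 times.

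A concentration taken about 1.5 hours after an oral dose is hard to interpret without the time of that dose. Concentration summaries by nominal time need it to check the window, and the population PK and exposure-response analyses in Section 8.4.4 need it as an input. The stake is the usability of these samples for a secondary objective.

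**Working it through.** The plan states no figure to reproduce here. The check sets the 7.7.1 list against the two tables.

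| Day | Postdose sample, Table 12 | Postdose sample, Table 13 | On the 7.7.1 list |
|---|---|---|---|
| C1D1 | yes | yes | yes |
| C1D15 | yes | no | yes |
| C2D1 (or escalation day) | only as a repeat after emesis on C1D15 | yes | no |
| C3D1 | no | yes | no |

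**Coverage.** For scheduled postdose days, the list covers 2 of 2 under Table 12 and 1 of 3 under Table 13. Even under Table 12 it misses the Cycle 2 Day 1 repeat after emesis.

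**Samples per patient.** Table 13 has one postdose sample at each of three days. Those on unlisted days number 3 − 1 = 2.

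**Samples at 600 mg.** Escalation is no earlier than Cycle 2 Day 1, so an escalated patient has at most two scheduled postdose samples at 600 mg (escalation day and Cycle 3 Day 1). None of the two is on a listed day.

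**Upper limit across Phase 2.** With n patients all reaching Cycle 3 Day 1, 2n of 3n postdose samples fall on unlisted days: 100 of 150 at n = 50, and 200 of 300 at n = 100. The number at 600 mg is at most 2 × (patients escalated). The documents do not give the number escalated.

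**Other sources of the clock time:**

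- The predose rule covers the previous dose, not the one that precedes the postdose sample. At the escalation visit, the previous dose is a 450 mg dose.
- The diary (Section 6.1) lists dose, date and missed doses, but not time of day.
- On PK days the morning dose is taken at the site after the predose draw, and Table 13 puts that draw within 30 minutes of the dose. The dose time is thus bracketed to a 30-minute interval. The postdose window is 1.5 hours ± 15 minutes, that is 75 to 105 minutes, also 30 minutes wide. If the two draws are d minutes apart, elapsed time lies between d − 30 and d. Only at d = 105 is that whole range inside the window. The bracket also assumes that the predose window was kept, which cannot itself be checked without the dose time.

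No section of either document requires the morning-dose clock time to be recorded at Cycle 2 Day 1 or Cycle 3 Day 1 under Table 13.

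**The case against.** The strongest reply is that the governing condition in 7.7.1 is any day with postdose PK sampling, and the bracket only glosses it. Under Table 13, Cycle 2 Day 1 and Cycle 3 Day 1 meet that condition, so a sensible site would record the time. This stands as far as it goes: missing times are possible, not inevitable, and the PK eCRF is not among the documents. But the bracket is worded as a complete list and is introduced as the only need, and a form built from it would omit the two days.

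Four stronger readings are tempting, and the documents do not support them:

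- **That the samples cannot be assigned to 450 or 600 mg.** The diary records dose and date, Section 6.4 sends deviations from the regimen to the eCRF, and SAP 6.5.3 and 6.5.3.1 derive actual dose and dose modifications from CRF dosing data. At Cycle 3 Day 1 the predose information also carries the previous dose amount.
- **That the dose time is lost for good.** Staff give the dose on site, need its time to draw at 1.5 hours, and need it again for the 2-hour ECG on Day 1 of each cycle (Table 10). Site source may hold it, although nothing requires that.
- **That vomiting is recorded on Cycle 1 Day 1 and Day 15 alone.** The sentence on the PK eCRF contains no such restriction. Sampling problems in general go to the eCRF, and vomiting reported as an adverse event goes to the AE CRF. What remains is a mismatch: the PK eCRF is not told to capture the 24 hours before the Cycle 2 and Cycle 3 predose samples, which the SAP flags need.
- **That 100 to 200 samples at 600 mg are at risk.** Those totals include patients who never escalate and assume that everyone reaches Cycle 3 Day 1.

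It is also fair to say that exclusion of a flagged concentration is discretionary. In addition, the SAP's own sampling table (Table 5) follows Table 12, so its window check has no scheduled postdose entry for these two days. The flag for a non-calculable elapsed time does not depend on that table.

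**Conclusion.** The contradiction between 7.7.1 and Table 13 is real and bears on the schedule in use. If the list is followed, the clock time of the morning dose may go unrecorded for 2 of 3 scheduled postdose samples per patient, including every scheduled postdose sample at 600 mg (at most two per escalated patient). Elapsed time could then be non-calculable for the samples meant to show exposure after escalation.

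The point is limited to that. It concerns the dose time more than the dose amount, a risk of missing data rather than certain loss, and the secondary PK objective with its exposure-response work. BMRR is not affected. The conclusion assumes that the PK eCRF was built to the 7.7.1 list and that no other instruction, such as the Laboratory Manual, requires the time. Neither document can be checked here. A correction is worthwhile because a time that is not in source cannot be reconstructed precisely and the change is small.

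**What to change.** In Protocol 7.7.1:

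1. Replace the bracketed days with: *all days with postdose samples in Table 12 or Table 13, including the escalation day and any Cycle 2 Day 1 repeat after emesis*.
2. Have the PK eCRF capture the morning-dose time and amount on all those days.
3. Align the PK eCRF vomiting record with the SAP flags for Cycle 2 Day 1 and Cycle 3 Day 1, including the 24 hours before a predose sample.

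For patients already sampled at those visits, ask sites to retrieve the dose time from source where it exists.

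The cost is two sentences in 7.7.1 and a PK eCRF setting, plus the queries to sites. No samples or visits are added. Correcting the SAP's sampling table alone would not solve this, because the gap is in what the protocol tells sites to record.

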7.8. Pharmacodynamics

Pharmacodynamic parameters are not evaluated in this study.

CCI

[REDACTED]

[REDACTED]

[REDACTED]

[REDACTED]

CCI [REDACTED]

[REDACTED]

[REDACTED]

CCI [REDACTED]

[REDACTED]

[REDACTED]

[REDACTED]

[REDACTED]

[REDACTED]

7.10. Patient-reported Outcomes

Patient-reported outcomes are not evaluated in this study.

7.11. Unscheduled Visits

Unscheduled study visits may occur at any time if medically warranted. Any assessments performed at those visits will be recorded in the eCRF.

7.12. End of Treatment and/or Early Termination

When the patient permanently discontinues study treatment, whether the patient is terminating the study early or the patient has completed the study, the EOT evaluations must be conducted. If the EOT visit coincides with a regular study visit, the EOT evaluations will supersede those of the scheduled visit and the data will be entered in the EOT visit in the eCRF. The patient should be encouraged to return for the 30-Day Follow-up Visit.

8. STATISTICAL CONSIDERATIONS

A detailed SAP will be prepared by the Sponsor or designee. This plan may modify the statistical methods outlined in the protocol; however, any major modifications of the primary endpoint definition or analysis will also be described in a protocol amendment.

8.1. Statistical Hypotheses

The primary endpoint of the study is BMRR per mRECIST v1.1. The study is designed to test the null hypothesis of $BMRR \leq 30\%$, which is considered not clinically meaningful and insufficient to warrant further study. The alternative hypothesis is the true BMRR for this patient population is at least 50%. This hypothesis applies to both the high-dose treatment arm and the standard dose treatment arm and will be tested using an exact binomial test at a one-sided 5% significance level.

8.2. Sample Size Determination

Safety Lead-in

During the Safety Lead-in, the first 9 evaluable patients will be enrolled to receive the high-dose encorafenib + binimetinib combination therapy. The high-dose treatment will be considered tolerable if the observed Cycle 1 DLT rate is $< 33\%$ (i.e., < 3 patients with DLTs out of 9 patients). Table 14 provides a comparison of the characteristics for this dose-escalation rule with 9 patients and the traditional 3 + 3 rules.

Table 14. Characteristics of Safety Lead-in Criteria for Cycle 1 Dose-limiting Toxicity Rate

True Cycle 1 DLT Rate	Probability of Dose Declared Toxic Using 3 + 3 Rules	Probability of Observed Cycle 1 DLT Rate $\geq 33\%$ in 9 Patients
10%	0.094	0.053
20%	0.291	0.262
30%	0.506	0.537
40%	0.691	0.768
50%	0.828	0.910

If the Sponsor and Investigators determine that the high-dose treatment is safe in the 9 evaluable patients, randomization will start for the Phase 2 portion of the study. Otherwise, no patients will be enrolled into the high-dose treatment Arm in Phase 2.

Phase 2

The sample size calculation of Phase 2 portion of the study is based on the primary endpoint of BMRR per mRECIST v1.1. The hypothesis to be tested and details of testing strategy are described in [Section 8.1](#).

If the high-dose treatment is determined to be safe in the Safety Lead-in phase, approximately 100 eligible patients will be randomized in a 1:1 ratio, stratified by baseline tumor burden in the brain (1 to 2 brain lesions vs. ≥ 3 brain lesions at baseline assessment) and by prior local therapy (yes vs. no) to the standard-dose and the high-dose treatment arm (i.e., approximately 50 patients per treatment arm). No formal statistical comparison will be performed between the 2 treatment arms and the statistical analysis will be performed separately by treatment arm.

If the high-dose treatment is determined not to be safe in the Safety Lead-in phase, no patients will be enrolled into the high-dose treatment arm. Up to 100 eligible patients will be enrolled into 2 cohorts in the standard-dose treatment arm. Phase 2 enrollment will close when either Cohort 1 or 2 reaches the enrollment of 50 patients.

- **Cohort 1:** Patients with locally confirmed *BRAFV600* cutaneous melanoma with metastases to the brain confirmed by MRI, asymptomatic, and *with* prior local therapy (e.g., SRS or SRT).
- **Cohort 2:** Patients with locally confirmed *BRAFV600* cutaneous melanoma with metastases to the brain confirmed by MRI, asymptomatic, *without* prior local therapy (e.g., SRS or SRT).

No formal statistical comparison will be conducted between the 2 cohorts.

Assuming a true BMRR $\geq 50\%$, the null hypothesis of BMRR $\leq 30\%$ will be rejected if at least 21 brain metastasis responses per mRECIST v1.1 are observed in a cohort of 50 patients. With approximately 50 eligible patients, the study will provide approximately 90% power at a one-sided 5% significance level.

